4.2 SCIENTIFIC RATIONALE FOR STUDY DESIGN

This study seeks to assess the degree to which IOVL used in conjunction with routine IOLNM provides additional data on nerve integrity and vocal cord function for patients undergoing neck procedures that place the recurrent and superior laryngeal nerve at risk for injury or postoperative dysfunction.

4.3 JUSTIFICATION FOR INTERVENTION

Currently, the use of IOLNM is based on audio cues, and visual assessment of external laryngeal muscle movement during surgery in response to stimulation, but not direct assessment of vocal cord movement is routinely possible. This information can be ambiguous and subject to judgement of the surgeon. The addition of IOVL provides direct assessment to vocal cord movement in response to stimulus, and may be useful in light of ambiguous IOLNM data, or limited visualization of external laryngeal muscles.

4.4 END-OF-STUDY DEFINITION

The end of the study for a participant is define as completion of the 3-month follow-up visit.

5 STUDY POPULATION

5.1 INCLUSION CRITERIA

In order to be eligible to participate in this study, an individual must meet all of the following criteria:

1. Age 18 and older with capacity to make all medical decisions
2. Medical indication for partial or total thyroidectomy, re-operative parathyroidectomy, or neck dissection

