Endpoints* :	
This is a descriptive study. There are no specific patient outcome endpoints. We will be primarily assessing the frequency with which the IOVL provides additional data to IOLNM which may be used to make further surgical decision making.

Study Population:	
125 patients over the age of 18 with a medical indication for partial or total thyroidectomy, re-operative parathyroidectomy, or neck dissection will be enrolled at Mount Sinai Hospital, Mount Sinai Beth Israel, Mount Sinai Morningside, and Mount Sinai West.

Phase* or Stage:	
Enrolling

[figure not shown]

Description of Sites/Facilities Enrolling Participants:	The Mount Sinai Hospital, Mount Sinai Beth Israel, Mount Sinai Morningside, Mount Sinai West
Description of Study Intervention/Experimental Manipulation:	Intraoperative video laryngoscopy will be used in conjunction with routine intraoperative nerve monitoring. We seek to asses the degree to which this will provide additional data on nerve integrity and vocal cord function for patients undergoing neck procedures that place the recurrent and superior laryngeal nerves at risk for injury or postoperative dysfunction.
Study Duration* :	We expect the study to take approximately 3 years.
Participant Duration:	3 months

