Patients who are undergoing bilateral procedures may benefit from the addition of video laryngoscopy. At times, the decision to proceed with the second half of a procedure is made based on the perceived integrity of the recurrent laryngeal nerve. There are times when the intraoperative nerve monitor provided ambiguous data about nerve integrity, or has equipment malfunction or failure and no data are available. Video laryngoscopy may give direct information about vocal cord function, and confirmation of vocal cord function in the setting of ambiguous data from the nerve monitor may prompt surgeons to proceed with surgery, or terminate without performing contralateral procedures, based on demonstrated vocal cord function.

This represents a pilot study to first describe the use of IOVL in conjunction with IOLNM during thyroid and reoperative parathyroid procedures.

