3 OBJECTIVES AND ENDPOINTS

OBJECTIVES	ENDPOINTS	JUSTIFICATION FOR ENDPOINTS
Primary 
We seek to assess the degree to which intraoperative video laryngoscopy used in conjunction with routine intraoperative nerve monitoring provides additional data on nerve integrity and vocal cord functions for patients undergoing neck procedures that place the recurrent and superior laryngeal nerves at risk for injury or postoperative dysfunction.
	
As this is a descriptive study, there are no specific patient outcome endpoints. We will be primarily assessing the frequency with which the IOVL provides additional data to IOLNM which may be used to make further surgical decisions.
	
We hope that the addition of IOVL will aid in surgical decision-making and nerve monitoring.

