4 STUDY DESIGN

4.1 OVERALL DESIGN

This will be a prospective cohort study without randomization. Patients enrolled will undergo the planned procedure according to our routines of care. IOLNM will be performed per our routine of care.

Additional procedures will involve the following:

- 1) Following consent, but prior to the operation we will complete routine in-office fiberoptic laryngoscopy to assess baseline vocal cord function
- 2) Prior to intubation, the patient will receive glycopyrrolate 0.004 mg/kg, as per typical pre-anesthetic dosing regimen, to decrease airway and mucous membrane secretions
- 3) Upon intubation, the video laryngoscope will be passed under direct vision and secured alongside the endotracheal tube. Vocal cords will be positioned in the visual field of the laryngoscope before beginning the operation
- 4) Following video laryngoscopy, and initiation of the procedure, the ipsilateral vagus nerve will be tested using nerve stimulation (per standard protocol) to ensure good distal nerve conduction and identify potential non-recurrent laryngeal nerve anatomy
- 5) At all points during the procedure where intraoperative nerve monitoring is used, information about vocal cord motion from video laryngoscopy will also be recorded. Specifically, we will record the neuropraxia index from the nerve monitor, and whether vocal cord function is concordant with the neuropraxia index
- 6) At the conclusion of resection, the recurrent and superior laryngeal nerves will be assessed with IONM, the vagus will be assessed with IONM, and lastly the vocal cords will be assessed with IOVL. This sequence is consistent with the describe protocol for IONM for testing the vagus and recurrent nerve prior to resection, and then again in reverse order following resection (V1R1R2V2).
- 7) After conclusion of the procedure and final surgical closing, prior to extubation, vocal cord function will again be assessed with video laryngoscopy
- 8) At standard 1-week and 3-month post-operative follow-up we will also perform routine fiberoptic laryngoscopy, per common practice, to assess vocal cord function. Patients will be asked to complete a brief questionnaire at both of these visits

Medical records will be used to collect the vast majority of data required for this study. In addition, patients will be asked to complete a brief questionnaire at both the standard 1-week and 3-month follow up visits.

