5.5 STRATEGIES FOR RECRUITMENT AND RETENTION

We typically see and operate on 20-25 patients per month in our endocrine surgery practice who undergo thyroid or re-operative parathyroid surgery in whom IOLNM is routine. Over a one-year period this would give us access to 200-250 patients who would meet inclusion criteria. Assuming approximately 25-50% of patients consent to participate, this should comfortably allow us to recruit 75-125 patients over the proposed study period. Based on our experience suggesting a 10-15% incidence of IOLNM system malfunction or failure, this should allow us 8-15 patients with IOLNM malfunction with which to directly compare and describe the information available to the surgeon from routine IOLNM and from the IOVL. The degree to which this information differs will allow us to determine if we think IOVL may provide information that could change outcomes and if further, larger studies are warranted.

Patients will be approached to consent in any one of the clinic spaces used by the investigators on this study. All of these locations are listed above. All surgical procedures will be performed in the operating rooms at Mount Sinai Hospital, Mount Sinai Morningside, Mount Sinai West, and Mount Sinai Beth Israel. Follow up visits will be at the previously described clinic locations.

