10.1.1.2 CONSENT PROCEDURES AND DOCUMENTATION

A member of the study team identifies potential study subjects from the review of the clinic and/or operating room schedules of study physicians. A HIPAA waiver is being requested for access to this information during this pre-screening process. Potential subjects are first approached by their treating physician during a routine office visit, to assess interest in the study. If the patient expresses interest, a member of the study team will approach them for an informed consent process following Mount Sinai SOP. If patients prefer to spend extra time going over the consent form, they can also consent for participation immediately before the surgical procedure. However in this case, even if the patient has already been informed of the study they will still go through the entire document with a member of the research team before signing. Patients are considered to be enrolled in the study after signing the ICF.

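### Does the lack of a planned-IOLNM criterion in 5.1, with enrolment dated at consent, let the 125 places go to patients who cannot inform the primary question?

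*Protocol*

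**What the plan says.** - **Eligibility.** Section 5.1 has two criteria: age 18 or older with capacity, and "Medical indication for partial or total thyroidectomy, re-operative parathyroidectomy, or neck dissection". Section 5.2 excludes only minors and people who cannot decide or consent. Neither section mentions IOLNM. The synopsis population also includes neck dissection ("re-operative parathyroidectomy, or neck dissection will be enrolled at Mount Sinai Hospital").
- **Scope.** The purpose statement in the synopsis (1.1) is about neck procedures in which IOLNM is used as routine, and gives thyroidectomy and re-operative parathyroidectomy as examples. The last sentence of 2.2 is narrower: "This represents a pilot study to first describe the use of IOVL in conjunction with IOLNM during thyroid and reoperative parathyroid procedures".
- **Recruitment pool.** Section 5.5 counts patients "who undergo thyroid or re-operative parathyroid surgery in whom IOLNM is routine" and says of them that "this would give us access to 200-250 patients who would meet inclusion criteria".
- **Primary measure.** Section 3 gives "the frequency with which the IOVL provides additional data to IOLNM which may be used to make further surgical decisions".
- **Conduct.** Section 4.1 says that "IOLNM will be performed per our routine of care". Its steps 4 to 6, repeated in 6.1.2, describe vagus stimulation, recording of the monitor's index alongside cord motion, and a closing assessment with the monitor.
- **Counting.** The synopsis speaks of 125 patients enrolled. Section 10.1.1.2 says "Patients are considered to be enrolled in the study after signing the ICF". Section 5.4 classes as screen failures those who consent but are then not assigned to the intervention or not entered.

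**The concern.** The primary measure needs both systems in the same operation. A patient operated on without IOLNM, or who consents and never has IOVL, contributes nothing to it. Read alone, 5.1 would let a screener accept a neck dissection for which no monitoring is planned. Read alone, 10.1.1.2 would let someone who signs the form and never reaches the operation use up one of the 125 places. The scope sentence in 2.2 and the pool in 5.5 leave out neck dissection, so the entry rule is wider than the population on which recruitment was planned.

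A later choice of analysis set could drop such patients but could not give their places back. The study would then report on fewer than 125 informative patients. If all 125 were kept in the denominator, the reported frequency would be too low.

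**Working it through.** **1. Is an unmonitored patient really admitted?** Section 5.1 is silent on IOLNM, but three other places are not. The purpose statement limits the study to procedures in which IOLNM is routine. Section 4.1 says IOLNM will be performed; the reference to routine of care is most naturally read as saying how. Steps 4 to 6 of 4.1, and 6.1.2, make no exception for unmonitored participants, so an operation without IOLNM could not follow the protocol as written. Section 5.5 treats IOLNM as routine in thyroid and re-operative parathyroid surgery. That leaves only a neck dissection done without IOLNM, and the protocol does not say that this practice performs such operations or would recruit from them.

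**2. Do 10.1.1.2 and 5.4 contradict each other?** The first, under consent procedures, says when a person becomes a study subject. The second applies to people who have already consented and describes a later step. A patient can be enrolled at signature and later be classed as a screen failure. That the 125 are counted at consent is an inference from joining the synopsis to 10.1.1.2. No section makes the 125 consented patients the denominator.

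**3. The plan's own yield figure.** Section 5.5 expects 8-15 malfunction cases from 75-125 recruits, at 10-15%.
- Lower end: 75 × 0.10 = 7.5, about 8, as stated.
- Upper end: 125 × 0.15 = 18.75, not 15. The stated 15 corresponds to 100 × 0.15 or 125 × 0.12.

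The upper end is therefore not reproduced. That is a separate matter, and nothing here depends on it.

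**4. How large could the loss be?** Let f be the share of the 125 places taken by patients without IOLNM or without IOVL. The documents give no value, so f is assumed. Informative patients = 125(1 − f); expected malfunctions = that number × 0.10 to 0.15. The intervals are exact (Clopper-Pearson) 95% intervals for an example frequency of about 15%.

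| f (assumed) | Informative patients | Expected malfunctions | Example | 95% interval | Width (points) |
|---|---|---|---|---|---|
| 0 | 125 | 12.5-18.75 | 19/125 | 9.4-22.7% | 13.3 |
| 10% | 112 | 11.2-16.8 | 17/112 | 9.1-23.2% | 14.1 |
| 20% | 100 | 10-15 | 15/100 | 8.6-23.5% | 14.9 |

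At f = 20% the interval is 14.9 − 13.3 = 1.6 points wider. The 100 patients lie inside the planned 75-125, and the 10-15 malfunctions inside the stated 8-15. To fall below 75 informative patients, f would have to exceed 1 − 75/125 = 40%.

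**5. Dilution.** With all 125 in the denominator, a true 15% would read as 15% × (1 − 0.20) = 12% at f = 20%. The protocol does not prescribe that denominator. A frequency of added information over IOLNM has no meaning in a patient without IOLNM, so an analyst would leave such patients out of it.

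**The case for a change.** The strongest case for a change is that entry rules and the point of enrolment belong to the protocol and cannot be repaired at analysis. Section 5.1 lists what an individual must meet, so a screener who applied it literally could accept an unmonitored neck dissection without breaking it. Consent may be taken at an office visit before surgery, so some patients will plausibly sign and never receive IOVL. Section 5.5 looks to a handful of malfunction cases to judge whether larger studies are warranted, so each lost place has some value. A criterion asking for planned IOLNM would cost one line.

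It stands that 5.1 lacks this line, that 2.2 and 5.5 omit neck dissection, and that 10.1.1.2 and 5.4 could be tied together more clearly. The step from there to lost information does not stand. It needs unmonitored operations that the protocol does not describe, or a counting rule that it does not state. Sections 9.1 and 9.2 set no hypothesis or sample size, so there is no precision target to miss.

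Counting the 125 only from patients in whom both systems were attempted also has a price. In a pilot meant to describe the use of IOVL, a consented patient in whom insertion was never attempted is feasibility information. Such a rule would replace that patient in the 125 and make the case less visible.

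**Conclusion.** The concern is accurate about the wording of 5.1 but does not call for a change. Followed as a whole, the protocol yields nerve-monitored patients and a sound descriptive frequency. The missing criterion and the uneven mention of neck dissection are drafting slips that the purpose statement and the procedures already resolve. The enrolment sentence and the screen-failure definition can both hold.

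No effect on a stated figure is shown. At an assumed 20% of places lost, the study keeps 100 informative patients and 10-15 expected malfunctions, and an interval around 15% is 1.6 points wider.

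This rests on two assumptions: that the investigators apply sections 4.1 and 6.1.2 to every participant, and that those who never have both systems are left out of the denominator. The true share of such patients is unknown. Only above 40% would the number of informative patients fall below the planned range.

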5.2 EXCLUSION CRITERIA

An individual who meets any of the following criteria will be excluded from participation in this study:

1. Patients who are under the age of 18, or who are not able to make medical decisions or consent to research

5.3 LIFESTYLE CONSIDERATIONS

N/A

5.4 SCREEN FAILURES

Screen failures are defined as participants who consent to participate in this study but are not subsequently assigned to the study intervention or entered in the study. Individuals who do not meet the criteria for participation in this trial (screen failure) because of meeting one or more exclusion criteria that are likely to change over time may be rescreened. Rescreened participants will be assigned the same participant number as for the initial screening.

5.5 STRATEGIES FOR RECRUITMENT AND RETENTION

We typically see and operate on 20-25 patients per month in our endocrine surgery practice who undergo thyroid or re-operative parathyroid surgery in whom IOLNM is routine. Over a one-year period this would give us access to 200-250 patients who would meet inclusion criteria. Assuming approximately 25-50% of patients consent to participate, this should comfortably allow us to recruit 75-125 patients over the proposed study period. Based on our experience suggesting a 10-15% incidence of IOLNM system malfunction or failure, this should allow us 8-15 patients with IOLNM malfunction with which to directly compare and describe the information available to the surgeon from routine IOLNM and from the IOVL. The degree to which this information differs will allow us to determine if we think IOVL may provide information that could change outcomes and if further, larger studies are warranted.

Patients will be approached to consent in any one of the clinic spaces used by the investigators on this study. All of these locations are listed above. All surgical procedures will be performed in the operating rooms at Mount Sinai Hospital, Mount Sinai Morningside, Mount Sinai West, and Mount Sinai Beth Israel. Follow up visits will be at the previously described clinic locations.

6 STUDY INTERVENTION(S) OR EXPERIMENTAL MANIPULATION(S)

6.1 STUDY INTERVENTION(S) OR EXPERIMENTAL MANIPULATION(S) ADMINISTRATION

6.1.1 STUDY INTERVENTION OR EXPERIMENTAL MANIPULATION DESCRIPTION

Intraoperative video laryngoscopy will be used in conjunction with routine intraoperative nerve monitoring. We seek to assess the degree to which this will provide additional data on nerve integrity and vocal cord function for patients undergoing neck procedures that place the recurrent and superior laryngeal nerves at risk for injury or postoperative dysfunction.

6.1.2 ADMINISTRATION AND/OR DOSING

At the patient's standard of care surgery, prior to intubation, the patient will receive glycopyrrolate 0.004 mg/kg, as per typical pre-anesthetic dosing regimen. Upon intubation, the video laryngoscope will be passed under direct vision and secured alongside the endotracheal tube. Vocal cords will be positioned in the visual field of the laryngoscope before beginning the operation. Following video laryngoscopy, and initiation of the procedure, the ipsilateral vagus nerve will be tested using nerve stimulation (per standard protocol) to ensure good distal nerve conduction and identify potential non-recurrent laryngeal nerve anatomy. At all points during the procedure where intraoperative nerve monitoring is used, information about vocal cord motion from video laryngoscopy will also be recorded. Specifically, we will record the neuopraxia index from the nerve monitor, and whether vocal cord function is concordant with the neuopraxia index. At the conclusion of resection, the recurrent and superior laryngeal nerves will be assessed with IONM, the vagus will be assessed with IONM, and lastly the vocal cords will be assessed with IOVL. This sequence is consistent with the described protocol for IONM for testing the vagus and recurrent nerve prior to resection, and then again in reverse order following resection (V1R1R2V2). After conclusion of the procedure and final surgical closing, prior to extubation, vocal cord function will again be assessed with video laryngoscopy.

6.2 FIDELITY

6.2.1 INTERVENTIONIST TRAINING AND TRACKING

N/A

6.3 MEASURES TO MINIMIZE BIAS: RANDOMIZATION AND BLINDING

N/A

6.4 STUDY INTERVENTION/EXPERIMENTAL MANIPULATION ADHERENCE

N/A

6.5 CONCOMITANT THERAPY

N/A

6.5.1 RESCUE THERAPY

N/A

7 STUDY INTERVENTION/EXPERIMENTAL MANIPULATION DISCONTINUATION AND PARTICIPANT DISCONTINUATION/WITHDRAWAL

7.1 DISCONTINUATION OF STUDY INTERVENTION/EXPERIMENTAL MANIPULATION

N/A

7.2 PARTICIPANT DISCONTINUATION/WITHDRAWAL FROM THE STUDY

Participation in this study is completely voluntary. Subjects are free to withdraw their participation at any time. Subjects who wish to withdraw from the study must contact the Principal Investigator or the research staff. Requests to withdraw from the study must be done in writing to the Principal Investigator at the address provided on the consent form.

The Principal Investigator or the institution may end a subject's involvement in the research study at any time without consent from the subject. This may be because the research study is being stopped, the instructions of the study team have not been followed by the subject, the investigator believes it is in the subject's best interest, or for any other reason.

7.3 LOST TO FOLLOW-UP

N/A

8 STUDY ASSESSMENTS AND PROCEDURES

8.1 ENDPOINT AND OTHER NON-SAFETY ASSESSMENTS

Data will be stored in the secure REDCap database. The study investigators will have access to the study data, which will be stored on a Mount Sinai secured, shared network drive. All paper documents relating to the study will be stored in the Research Office. The data will be stored with a code that can be linked to the identity of the participant.

Duration the data will be stored: The Principal Investigator will keep the data on a mass storage device, Mount Sinai's server, for a minimum period of six years after publication.

All study data collected will be entered into the electronic REDCap database. The data will be stored on a Mount Sinai network drive, accessible only to the PI and members of the research team. The data will be password protected.

Data is always de-identified prior to data analysis. In all disclosures outside of Mount Sinai, subjects are not identified by name, social security number, address, telephone number, or any other direct personal identifier unless disclosure of the direct identifier is required by law.

All data analysis will be done on de-identified data only and on a secure Mount Sinai Network computer.

All discussions with patients will be conducted in a private area away from distractions, in order to maintain patient privacy. The patient will have control of/be responsible for scheduling their appointments at a time that is convenient for them. In order to make the subject feel "at ease," study personnel will be accessible, available, and receptive to questions and concerns raised by the patient about study-related procedures.

If subjects are injured or made sick from taking part in this research study, medical care will be provided. Generally, this medical care will be billed to the subject and/or their health care insurance. In the event of injury, subjects should contact the Principal Investigator, [name].

